6.3.2.2. Prohibited Medications

A list of prohibited medications is provided in [Table 1](#).

Table 1: Prohibited Medications

Drug Class	Prohibited Agents
Prohibited inflammatory bowel disease medication	
Corticosteroids (intravenous) ^a	
TNF alpha agonist	Infliximab, adalimumab, golimumab, certolizumab, or biosimilar agent
Integrin antagonist	Vedolizumab and natalizumab
Interleukin antagonist	Ustekinumab
JAK inhibitor	Any JAK inhibitors including, but not limited to, tofacitinib, baricitinib, and upadacitinib
Other (nonbiologics)	Cyclosporine, thalidomide, tacrolimus, ozanimod, leflunomide and any investigational agent
Investigational biologics	Any investigational biologic agent
Lymphocyte-depleting therapies	Alemtuzumab, cyclophosphamide, total lymphoid irradiation, rituximab, and any other lymphocyte-depleting therapy
Other prohibited Medications	
Chronic nonsteroidal anti-inflammatory drugs (NSAIDs) ^b	Aspirin, ibuprofen, naproxen, diclofenac, indomethacin, cyclooxygenase-2 (COX-2) inhibitors
Other biologics	Antibody based or other systemic biologics, e.g. denosumab, trastuzumab

^a Oral and/or rectal corticosteroids may be used in case of a flare (see Section 5.1), and oral corticosteroids should not exceed prednisone 30 mg/day equivalents (except for at least 12 weeks prior to screening and including baseline of the present study).

^b Occasional use for transient symptoms and daily use of aspirin up to 162.5 mg for the purpose of cardiovascular prophylaxis are permitted

6.3.3. Food and Beverage Restrictions

There are no specific food and beverage restrictions for this study. The IP can be taken with or without food. There are no specific requirements regarding IP and the dietary intake.

6.4. Measures to Minimize Bias

6.4.1. Randomization

Subjects will keep the subject number received in the SELECTION-LTE study. When a subject is confirmed to be eligible for the clinical study, the subject will be randomized. Allocation of each subject to a given treatment will be done using a centralized electronic system (randomization and trial supply management [RTSM]). Subjects will be randomized in a 1:1 ratio to 200 mg or 100 mg filgotinib q.d. Subjects will be stratified according to ES (score of 0 or 1) at baseline to ensure treatment balance in each stratum.

6.4.2. Blinding and Unblinding

This is a randomized, double-blind clinical study. The subjects and the entire clinical study team, including the investigators, clinical study coordinators, and sponsor personnel are blinded to

treatment assignment until the study primary analysis time point, with the exception of the sponsor's clinical study supply leader.

Unblinding will take place at the study primary analysis time point, i.e. after the last subject completed their Week 48 postbaseline visit or has completed their Week 12 post re-escalation visit (if baseline of re-escalation is within the first 48 weeks of the study), or after the last follow-up of subjects discontinuing prior to Week 48, whichever comes last. Unblinding at the Week 48 interim analysis is described in Section 9.3.2. In addition, [REDACTED]

[REDACTED] external functions specified in RTSM specification, will also be unblinded to treatment assignment.

Study medication provided to the sites will be packaged and labeled assuring the blinding of the IP. Unblinded study medication will be provided for treatment in case of re-escalation and for treatment after unblinding. Subjects who are re-escalated to 200 mg filgotinib q.d. will remain blinded to their treatment at randomization.

The blind can be broken only if the investigator deems it necessary for the safety of a subject. The investigator is encouraged to discuss considerations to break the blind with the medical monitor of the study, whenever possible and where the situation allows. However, the responsibility to break the treatment code in emergency situations resides solely with the investigator. The investigator is not required to discuss unblinding beforehand if he or she feels rapid emergency unblinding is necessary, but is required to inform the sponsor within 24 hours after unblinding has occurred.

The blind can be broken by the investigator via RTSM.

If the blind is broken for any reason during the course of the clinical study, all relevant information will be documented by the site. The reason for breaking the blind will be indicated and justified in the source documentation.

In case an AE leads to unblinding, that AE should be given as the reason for unblinding.

The pharmacovigilance department of the sponsor (or a representative thereof) may independently unblind cases for expedited reporting of suspected unexpected serious adverse reactions (SUSARs) to worldwide regulatory agencies (see Section 11.4).

7. INVESTIGATIONAL PRODUCT

7.1. Identity of the Investigational Product

Filgotinib is available as 200 mg and 100 mg strength tablets. Filgotinib tablets, 200 mg and 100 mg are beige, debossed with "GSI" on one side and "200" or "100" on the other, capsule-shaped, biconvex, film-coated tablets for clinical use. Each tablet contains the equivalent of 200 mg or 100 mg filgotinib free base in the form of filgotinib maleate. In addition to the active ingredient, filgotinib tablets contain the following inactive ingredients: microcrystalline cellulose, lactose monohydrate, fumaric acid, pregelatinized starch, silicon dioxide, magnesium

stearate, macrogol/polyethylene glycol (PEG) 3350, polyvinyl alcohol, talc, titanium dioxide, iron oxide yellow, and iron oxide red.

Placebo-to-match (PTM) 200 mg and 100 mg filgotinib tablets are identical in appearance to the respective active filgotinib tablets. PTM 200 mg and 100 mg filgotinib tablets contain the following inactive ingredients: microcrystalline cellulose, lactose monohydrate, croscarmellose sodium, magnesium stearate, macrogol/PEG 3350, polyvinyl alcohol, talc, titanium dioxide, iron oxide yellow, and iron oxide red.

7.2. Dosage and Administration

The IP needs to be taken q.d. at approximately the same time. Subjects will be asked to swallow the IP with a glass of water and to not chew the drug prior to swallowing. The IP can be taken with or without food. There are no specific requirements regarding IP and the dietary intake.

Blinded treatment up to the primary analysis time point

Doses of 100 mg or 200 mg filgotinib, as a combination of 2 tablets (filgotinib and PTM) for blinding purposes, will be taken q.d. orally.

Subjects will be provided with medication kits containing 2 bottles with blinded IP, either:

- 100 mg filgotinib tablets in bottle 1 and PTM 200 mg filgotinib tablets in bottle 2;
- 200 mg filgotinib tablets in bottle 1 and PTM 100 mg filgotinib tablets in bottle 2.

At the baseline visit (Day 1), IP will be administered on-site after predose assessments have been completed. If on Day 1, the subject has already taken the IP as assigned in the SELECTION-LTE study, the first dose as assigned in this study should be taken on Day 2.

Starting from Day 2, subjects will be instructed to take 1 tablet from each bottle q.d. (i.e. a total of 2 tablets).

Re-escalation

Subjects who are re-escalated to open-label 200 mg filgotinib q.d. will be provided with bottles containing unblinded IP (200 mg filgotinib tablets in 1 bottle). If the subject has already taken IP on the re-escalation baseline day, the first adjusted dose should be taken on re-escalation Day 2. Subjects will be instructed to take 1 tablet q.d.

Subjects who are re-escalated continue on open-label 200 mg filgotinib q.d. for at least 12 weeks. If the subject does not respond to re-escalation therapy within a timeframe of maximum 12 weeks, the subject will be permanently discontinued from the treatment. If subject improvement is sufficient in the opinion of the investigator, the subject may continue on open-label 200 mg filgotinib q.d. until the end of the study.

After unblinding at the primary analysis time point

For continued q.d. treatment after unblinding until the end of the study, subjects will be provided with bottles containing unblinded IP, either:

- 1 bottle with 100 mg filgotinib tablets;
- 1 bottle with 200 mg filgotinib tablets.

Subjects will be instructed to take 1 tablet q.d.

At each IP dispensing visit, subjects will receive IP to take home on non-study visit days and will be provided with instructions for dosing. Multiple medication kits can be provided to ensure the subject has sufficient tablets to cover the period until the next visit when IP dispensing is scheduled.

If a subject misses a dose (e.g. because he/she forgot to take the medication), he/she should take the missed dose as soon as possible during the same day of the planned intake time, or else that dose should be skipped. If a dose is not taken it should be returned to the bottle.

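### As written, both blinded kits hold the active tablet in bottle 1, so if the bottle numbers can be recognised the strength marked on that tablet gives the randomized dose

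*Protocol*

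**What the plan says.** The study is a double-dummy comparison of two strengths. Section 6.4.1 states: "Subjects will be randomized in a 1:1 ratio to 200 mg or 100 mg filgotinib q.d". During blinded treatment each subject has two bottles and, per Section 7.2, "subjects will be instructed to take 1 tablet from each bottle q.d".

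Section 7.2 allows exactly two kit contents:

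- 100 mg arm: "100 mg filgotinib tablets in bottle 1 and PTM 200 mg filgotinib tablets in bottle 2"
- 200 mg arm: "200 mg filgotinib tablets in bottle 1 and PTM 100 mg filgotinib tablets in bottle 2"

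The synopsis (Investigational Product, Dosage, and Mode of Administration) repeats both lines.

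Section 7.1 says active tablets carry the number 200 or 100 on one face. On the placebos it says: "Placebo-to-match (PTM) 200 mg and 100 mg filgotinib tablets are identical in appearance to the respective active filgotinib tablets".

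Section 6.4.2 requires subjects, investigators, coordinators and sponsor personnel to be blinded until the primary analysis time point, with the supply leader as the named exception. Re-escalated subjects must stay blinded to the arm they were randomized to. Its safeguard is general: "Study medication provided to the sites will be packaged and labeled assuring the blinding of the IP". Section 7.3 describes white bottles of 30 tablets. It does not say whether a bottle number is printed on the label, and it gives no rule on bottle order.

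**The concern.** A double-dummy protects the blind only if each identifiable position in the kit looks the same in both arms. Here the bottle number follows active versus placebo, while the visible marking follows strength. Together they identify the arm.

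The tablets are seen routinely. Subjects take one from each bottle daily, and Day 1 dosing takes place on site unless the subject has already taken that day's parent-study dose (Section 7.2). Unused tablets and empty packages come back at every dispensing visit and are inventoried (Section 7.5). Site staff also hold the protocol, which contains the key.

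Several outcomes are open to knowledge of the dose. Stool frequency and rectal bleeding come from the subject's e-Diary, and the Physician's Global Assessment from the investigator (Section 8.3.2). Endoscopy is read locally (Section 8.3.1). The work-up for a flare starts from reported symptoms (Section 5.1), a subject may stop treatment on request (Section 5.4.1.1), and adverse event causality is the investigator's judgement (Section 11.2.1). Under the primary estimand in Section 4.1, both confirmed flare and treatment discontinuation before Week 48 count as nonresponse.

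**Working it through.** The plan gives no figure to reproduce. The check is to list what can be seen in each bottle by arm, and then ask what that reveals.

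**Inputs.** Kit contents from Section 7.2; strength marking and placebo appearance from Section 7.1; 1:1 allocation from Section 6.4.1.

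**Step 1. Visible marking under the layout as written.**

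| Arm | Bottle 1 | Bottle 2 |
|---|---|---|
| 100 mg | marked 100 (active) | marked 200 (placebo) |
| 200 mg | marked 200 (active) | marked 100 (placebo) |

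**Step 2. Bottles recognisable as 1 and 2.** Let A be assignment to the 100 mg arm and S be seeing 100 on the bottle 1 tablet. Then P(S | 100 mg arm) = 1, P(S | 200 mg arm) = 0 and P(A) = 0.5.

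P(A | S) = (0.5 × 1) / (0.5 × 1 + 0.5 × 0) = 1.

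By the same reasoning, a 200 on the bottle 1 tablet means the 200 mg arm with probability 1. A reader who knows the rule is right 100% of the time.

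**Step 3. Bottles not recognisable as 1 and 2.** Each subject has one bottle of tablets marked 100 and one marked 200, whichever the arm. The view is the same in both arms, so the chance of a correct guess is 0.5.

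**Step 4. Bottles defined by strength.** If one numbered bottle always holds the tablet marked 100 and the other always holds the tablet marked 200, then P(S | arm) is the same in both arms. With the 100-marked tablet in bottle 1:

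P(A | S) = (0.5 × 1) / (0.5 × 1 + 0.5 × 1) = 0.5.

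The blind then holds even with printed numbers and with the protocol in hand.

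**Step 5. Against the stated requirement.** Steps 2 and 3 differ in one fact only: whether the numbers can be recognised. Section 7.2 and the synopsis name the bottles by number. Sections 6.4.2 and 7.3 do not say the numbers are absent from the labels. The written layout is therefore compatible with Section 6.4.2 only under a condition that the documents do not state.

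**The case against.** The strongest reply is that 'bottle 1' and 'bottle 2' may be only a way of listing kit contents. No dosing instruction depends on the number, since subjects take one tablet from each bottle. Section 7.3 never says the labels carry numbers, and Section 6.4.2 says packaging and labeling assure the blind. If the numbers were not displayed, nothing is revealed. This stands as a limit on the finding. It does not repair the text, because a general assurance cannot be relied on when the one specific layout given would defeat it.

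Four stronger readings are tempting, and the documents do not support them.

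- *That the blind was broken.* A reader might infer this from the layout, but the label specification is not in the documents and nothing shows that anyone read the allocation.
- *That subjects knew they had been stepped down.* Site staff have the protocol. Nothing shows that subjects are told bottle 1 is active.
- *That the bias has a known size.* With the planned 40 per arm, one changed outcome moves a proportion by 1/40 = 2.5 points. The documents give no basis for how many outcomes would change, or in which arm, so no total follows. Some routes are also limited. An ES-confirmed flare needs an endoscopic increase of at least 1 point, so symptom reports alone cannot produce one. Corticosteroids added after re-escalation affect subjects who are already nonresponders under the primary estimand.
- *That a between-arm difference in remission or flare is compromised.* The SAP makes no such comparison. The study stopped with 22 randomized subjects (SAP 2.4.3), before any reached Week 48 (SAP 6.1). Remission and flare data are only listed (SAP 6.3.1.3 and 6.3.3).

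Early termination reduces the consequence but does not remove it. The SAP still describes the study as double-blind (SAP 2.2), summarizes CRP and FCP by arm (SAP 6.3.2) and tabulates adverse events by arm, including related events (SAP 6.4 and 6.4.1.8).

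**Conclusion.** Wrong as written, conditional on the bottle numbers being recognisable. If they are, the bottle 1 tablet identifies the randomized dose for every subject on a blinded kit, to anyone who knows the layout. The people most clearly in that position are site staff who handle dispensed and returned tablets, and Section 6.4.2 requires them to be blinded. If the numbers are not recognisable, the kits look alike and the blind is unaffected.

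The conclusion rests on three things: kits built as Section 7.2 describes, numbers that can be seen or inferred on the physical bottles, and a reader who has the protocol. The first is stated in the protocol, the third is true of site staff, and the second is undocumented. The point concerns the specification. It does not show that unblinding occurred, and no size of bias can be given.

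**What to change.** In Section 7.2, the synopsis and the kit and label specification, define the bottles by tablet strength in both arms. One numbered bottle always holds the tablet marked 100 (active in the 100 mg arm, placebo in the 200 mg arm). The other always holds the tablet marked 200 (active in the 200 mg arm, placebo in the 100 mg arm). Doses, tablets and counts do not change. Section 6.4.2 can then refer to this layout as the means by which the blind is kept.

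For kits already supplied, check the label specification and retained packaging to see whether bottle numbers were visible.

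- If they were, state in the abbreviated CSR that allocation could be read from the bottle number and tablet marking. Interpret the by-arm CRP, FCP and adverse event summaries, and the listed remission and flare data, with that in mind.
- If they were not, say so in one sentence.

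The cost is a wording correction and a change to the kit or label specification. For this terminated study, it is in practice one document check and a short CSR statement. No extra procedure, visit or subject is needed.

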7.3. Packaging, Labeling, and Distribution

Filgotinib and PTM filgotinib tablets are packaged in white, high-density polyethylene bottles. Each bottle contains 30 tablets, silica gel desiccant, and polyester packing material. Each bottle is enclosed with a white, continuous thread, child-resistant polypropylene screw cap fitted with an induction-sealed, aluminum-faced liner. The IP to be distributed to centers in the United States (US), EU, and other participating countries shall be labeled to meet applicable requirements of the US Food and Drug Administration, EU Guideline to Good Manufacturing Practice – Annex 13 (Investigational Medicinal Products), and/or other local regulations, as applicable.

The distribution of IP to the site will only occur after the required local documentation is obtained, including clinical study approval by regulatory authorities and the IECs/IRBs, documentation on which the assessment of the investigator's qualifications was based (e.g. curriculum vitae), and the signed and dated clinical study agreement.

In case of travel restrictions (including due to SARS-CoV-2 pandemic), to ensure study subjects maintain dosing per protocol requirements during this study, special delivery services through Direct to Patient (DTP) shipments of IP to the subject can be implemented. DTP shipments should only be used in case of emergency when on-site IP dispensation is not possible, and if allowed per local regulations. Local guidelines must be followed and regulatory approval or notification of authorities may be required. Agreement of the subject to receive IP at home is required prior to the shipment of IP to the subject's home. The DTP shipment process used will be reviewed and approved by the sponsor. In case the DTP shipments originate from the site they will be coordinated by the investigational site(s) in collaboration with the local CRO without the involvement of the sponsor, to ensure clinical study integrity.

7.4. Storage

Sites must store IP supplies in a secure temperature-controlled area at room temperature (15-25 °C; excursions permitted between 15 °C and 30 °C) until dispensed. Sites are required to monitor the storage temperature by using at least a min-max temperature recording device and to record each working day the minimum and maximum temperature (either by the temperature recording device or in a temperature log). This is to establish a record of compliance with these storage conditions. The investigator will instruct subjects how the IP should be stored at home.

7.5. Treatment Compliance and Drug Accountability

The investigator must discuss treatment compliance with the subject prior to the start of the study. Missed doses should be discussed to try to ascertain the reason(s). Every effort should be made to ensure the proper subject dose. Subjects with poor compliance will be retrained by the site. IP administration as indicated by the subject (amounts as well as periods) will be recorded on the case report form (CRF).

The pharmacist or designated clinical study staff will maintain a log (paper or electronic) of the total amount of IP received at site, amount dispensed to the subject, and the amount of IP returned by the subject to the site. IP supplies for each subject will be inventoried and accounted for throughout the clinical study. On an ongoing basis and at the end of the treatment period, these records will be checked against the inventory by the study monitor. All clinical supplies will be stored in locked facilities.

Subjects will return any unused IP and empty IP packages at every dispensing visit, unscheduled visit, and/or ED visit. All used and unused IP, and packages are to be returned from the sites and/or any vendor involved in the clinical study supplies management activities to the agreed location (depot), if possible. Only in exceptional cases, upon sponsor approval, IP can be destroyed at the site. All returns and destructions must be properly documented.

8. CLINICAL STUDY ASSESSMENTS

Every effort must be made to ensure that CSP-required tests and procedures are completed as described in the Schedule of Activities (see Section 8.9.1 and Section 8.9.2). To avoid inter-observer variability, every effort should be made to ensure that clinical observations are performed by the same individual who made the initial baseline determinations.

8.1. Timing of Assessments

The study assessments described below will be performed at time points as specified in the Schedule of Activities in Section 8.9.1 and Section 8.9.2.

The ICF needs to be signed before any study procedure, including screening procedure, is carried out.

Subjects in the SELECTION-LTE study who are in clinical remission with 200 mg filgotinib q.d. for at least 2 consecutive quarterly visits, will be provided the option to roll over to the present study at any scheduled visit of the SELECTION-LTE study or at a separate visit.

Subjects will be requested to attend the site for at least 2 screening visits:

- Screening visit 1 (ICF signature) (S1) and other screening assessments as per Schedule of Activities in Section 8.9.1, including TB assessment and screening FCP assessment (if last FCP observation was >6 months prior to screening or most recent FCP value was >250 µg/g) in order to obtain the results prior to randomization.

Depending on the screening FCP in the present study (if applicable) and the ES, the subject will either be a screening failure (FCP >250 µg/g or ES >1) in the present study and will remain in SELECTION-LTE, or the subject will be eligible (FCP ≤250 µg/g and ES ≤1) and will need to perform the EoT assessments in SELECTION-LTE and the remaining screening assessments before being randomized to the present study (refer to Schedule of Activities in Section 8.9.1).

- Screening visit 2 (S2), the EoT visit in SELECTION-LTE, and the Day 1 visit of the present study can occur on the same day or on 2 consecutive days.

Some data collected in SELECTION-LTE, as specified in the Schedule of Activities in Section 8.9.1, may be used in the present study.

In case a randomized subject is not able to attend a scheduled study visit on-site for reasons related to SARS-CoV-2 pandemic restrictions, a phone call or a televisit may be conducted (televisit after obtaining approval from the sponsor). It is strongly recommended to conduct planned study assessments for the applicable visit as per protocol as much as possible. If possible and if local regulations allow, and the subject agrees, trained site study staff are encouraged to perform study assessments at the study subjects' home or a local facility. Only staff trained in conducting the protocol planned assessments are authorized to perform home or local facility visit assessments and the alternative arrangements need to be adequately documented.

DTP shipments are possible, if needed, in case of travel restrictions (e.g. due to SARS-CoV-2 pandemic), and if allowed per local regulations (refer to Section 7.3).

